**Data Analysis and Statistics**

Twenty regions of interest (ROIs) were drawn on the CT scan from each session (SHAM and active) by the same investigator to locate the lower limb skeletal muscles. The muscles that comprise the knee extensors (rectus femoris, vastus medialis, vastus intermedius, and vastus lateralis) and knee flexors (semimembranosus, semitendinosus, long head of the biceps femoris, short head of the biceps femoris, gracilis, and sartorius) were identified via visual inspection in the upper leg, and the plantar flexors (gastrocnemius, soleus, peroneus longus, peroneus brevis, flexor digitorum longus, flexor hallucis longus, and tibialis posterior) and dorsiflexors (tibialis anterior, extensor digitorum longus, and extensor hallucis longus) were distinguished in the lower leg. Figure 2 displays a representative upper leg CT image with ROIs identified, a corresponding PET image, and the CT and PET images co-registered. As a result of FDG uptake occurring during the treadmill task, glucose uptake (GU) values closely reflect FDG uptake during the task. For each ROI, standardized uptake values (SUVs) were calculated based on the injected FDG dose and subjects' body weight. Despite the fasted state of the subjects, SUVs may be affected by varying insulin levels during Sessions 2 and 3. Therefore, SUV data were analyzed without normalization and as values normalized to the liver activity as a reference tissue. Moreover, SUV asymmetry indices (AIs) were calculated to determine the magnitude of asymmetry between the more- and less-affected legs with a previously used equation:  $((\text{less-affected side} - \text{more-affected side}) / ((0.5) \times (\text{less-affected side} + \text{more-affected side}))$ .

side))  $\times 100$ ). An AI value  $\geq 10\%$  was considered asymmetric. The relative distribution ((standard deviation / mean)  $\times 100$ ) of GU values in PET image voxels within each muscular ROI was calculated as an index of spatial glucose uptake heterogeneity (GUh). The data were analyzed using PMOD Version 4.001 (PMD Technologies LLC, Zurich, Switzerland).

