#### Statistical Analysis

Mean  $\pm$  standard deviation SUVs and GUh for each muscle group (i.e., knee extensors, knee flexors, plantar flexors, and dorsiflexors) were calculated for each subject, and statistical analyses were performed for each muscle group. Normality assumptions were evaluated by way of histograms, Q-Q plots, and the Shapiro–Wilk test. Because these assumptions were met, paired t-tests were performed for each participant to compare the muscle groups of each leg between conditions (e.g., left knee extensors during SHAM vs. left knee extensors during tDCS). Significance was accepted at  $p < 0.05$ , and Cohen's d effect size was calculated for all significant results. Analyses were performed using GraphPad Prism 8.1.2 (GraphPad Software, San Diego, CA, USA).

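### Cohen's d is described for results significant at an unadjusted p<0.05, with no effect size or confidence interval described for the rest, so reported effects would be biased upward if power was low or moderate

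*Combined protocol and SAP*

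**What the plan says.** The rule is in the Statistical Analysis section of the combined protocol and SAP. After the normality checks, "paired t-tests were performed for each participant to compare the muscle groups of each leg between conditions". "Significance was accepted at" p<0.05, and Cohen's "d effect size was calculated for all significant results". Means and SDs of SUV and GUh "were calculated for each subject, and statistical analyses were performed for each muscle group". No primary comparison is named and no multiplicity adjustment is described.

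The Data Analysis and Statistics section sets out the measures. Because "SUVs may be affected by varying insulin levels during Sessions 2 and 3", the "SUV data were analyzed without normalization and as values normalized to the liver activity as a reference tissue". In addition, the coefficient of variation "of GU values in PET image voxels within each muscular ROI was calculated as an index of spatial glucose uptake heterogeneity" (GUh). Asymmetry indices are also calculated, but no test is specified for them, so they are not counted here.

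The documents give no sample size, power, target effect or SD of the paired differences. They do not say which SD is the denominator of Cohen's d. They describe no confidence interval for any tDCS minus SHAM difference.

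**The concern.** If an effect size is reported once a comparison has passed p<0.05, the p-value acts as a filter on the estimate. When power is low or moderate, the comparisons that pass tend to be those where chance enlarged the observed difference, and the d attached to them is then too large on average. Someone planning a later trial from those values would make it too small.

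The comparisons that do not pass are left with no described estimate of effect or precision. A reader cannot then tell a small effect from one that was measured too imprecisely to judge. With many unadjusted tests, some of the results that receive a d may also be false positives.

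**Working it through.** There is no stated sample size, power or effect to reproduce, so the check shows how the rule behaves over an assumed range.

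**Inputs from the documents.** Paired t-test between SHAM and tDCS; level 0.05; 4 muscle groups; each leg tested; raw SUV, liver-normalised SUV and GUh.

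**Assumptions.** Two-sided test; participants are the pairs; d is d_z (mean paired difference divided by the SD of the paired differences); n from 8 to 30; true d_z from 0.5 to 1.0.

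**1. Number of comparisons.** 4 groups × 2 legs × 3 measures = 24. If no comparison has a true effect, 24 × 0.05 = 1.2 false positives are expected, whatever the correlation between tests. If one SUV version is only a sensitivity check, 4 × 2 × 2 = 16 and 16 × 0.05 = 0.8.

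**2. The filter.** Since t = d_z × √n, a comparison reaches p<0.05 only if |d_z| ≥ t(0.975, n−1)/√n:
- n=8: 2.365/2.828 = 0.84
- n=10: 2.262/3.162 = 0.72
- n=15: 2.145/3.873 = 0.55
- n=30: 2.045/5.477 = 0.37

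Under the rule as written, no d is described for anything below these values.

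**3. Effect of the filter.** For a true effect δ, the observed d_z is a noncentral t variable (n−1 df, noncentrality δ√n) divided by √n. The table gives the median absolute d_z among simulated results with p<0.05 (400,000 runs per setting).

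| Assumed true d_z | Assumed n | Power | Median reported absolute d_z |
|---|---|---|---|
| 0.5 | 8 | 0.23 | 1.08 |
| 0.5 | 10 | 0.29 | 0.93 |
| 0.5 | 15 | 0.44 | 0.74 |
| 0.5 | 30 | 0.75 | 0.57 |
| 0.8 | 10 | 0.62 | 1.03 |
| 0.8 | 30 | 0.99 | 0.81 |
| 1.0 | 10 | 0.80 | 1.14 |
| 1.0 | 15 | 0.95 | 1.04 |

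If every d is reported, the medians at true 0.5 are 0.518, 0.514 and 0.510 for n=8, 10 and 15. Selection therefore multiplies the typical value by 1.076/0.518 = 2.1, 0.928/0.514 = 1.8 and 0.741/0.510 = 1.5.

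Means show the same pattern. At n=10 and true 0.5, the mean d_z is 1.01 among significant results and 0.55 among all results. At n=30 and true 0.8, it is 0.83 and 0.82. The excess of 0.55 over 0.5 is ordinary small-sample bias in d, which full reporting does not remove.

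**4. A comparison that fails the filter.** Take an observed d_z of 0.5 at n=10. Then t = 0.5 × 3.162 = 1.58 and p = 0.148. The 95% CI for d_z, by noncentral t inversion, is −0.17 to 1.15. That is compatible with no effect and with a large one, but no such interval is described.

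**The case against.** The strongest reply is that the text does not contain the word only. This is a short methods extract, and its silence about intervals is weak evidence of what was finally reported. That stands: the restriction is inferred from a rule whose stated scope is the significant results, so the fair wording is that nothing is described for the others.

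The second reply is that the bias depends on power and disappears when power is high. This also stands. A reader might infer that the d values from this trial do overstate the true effects. The documents do not support that, because n, the SD and the true effect are not given and the larger figures above come from low-power settings. The values also assume d_z. Another denominator would change them, though not the selection on p.

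Third, a mean for each subject under each condition gives every paired difference, and so its SD and interval. That is correct, so the gap lies in the described reporting and not in the data or the tests.

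Finally, a reader might take the 24 unadjusted tests to mean that false-positive findings are present or that the p-values are invalid. Neither follows. The 1.2 is an expectation under no effect anywhere. The chance of at least one false positive, 1 − 0.95^24 = 71%, applies only to independent tests and is lower under positive correlation. Multiplicity is also a separate matter from the selection of effect sizes. It matters here because each false positive would receive a d.

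**Conclusion.** The point holds in conditional form. Followed as written, the rule selects effect sizes on an unadjusted p<0.05, and no effect size or interval is described for the remaining comparisons. The selected values are biased upward when power is low or moderate, by a factor of about 1.5 to 2.1 at an assumed true d_z of 0.5 with n=15 down to 8. The bias is negligible at high power.

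Its size in this trial cannot be determined from the documents. The count of 24 assumes that all three measures are tested and that participants are the pairs; the phrase about testing for each participant leaves the unit unclear. This is a reporting weakness that should be corrected. It does not invalidate any test.

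**What to change.** Take the participant as the unit of analysis and say so. For every comparison, whatever its p-value, report the mean tDCS minus SHAM difference with its 95% CI, and an effect size with its CI. Define the effect size, including which SD is the denominator. State the number of comparisons and that the p-values are unadjusted.

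The Statistical Analysis section is in the past tense and reports that the normality assumptions were met, so the data had already been examined. Full reporting remains possible, because it requires no choice among results.

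The cost is a longer results table: 24 rows if all three measures are tested. It uses values already calculated for each subject, needs no new data, changes no test and loses no power.
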